|--|--------------------------------------|----------------------------|----------------------|----------------------|---------------------|---------------------|-----------------------|---------------------|---------------------|----------------------------------|------------------------------------|----------------------------------|----------------------------------|---------------------|
| | | Day 1 Dosing Visit | Day 2 Telephone Call | Day 8 Telephone Call | Day 15 Clinic Visit | Day 29 Dosing Visit | Day 30 Telephone Call | Day 36 Clinic Visit | Day 43 Clinic Visit | Day 57 Dosing Visit ^b | Day 58 Telephone Call ^b | Day 64 Clinic Visit ^b | Day 71 Clinic Visit ^b | Day 91 Clinic Visit |
| Prior and concomitant medications | | <=====→ | | | | | | | | | | | | |
| Efficacy assessments | | | | | | | | | | | | | | |
| Serum PSA | X | X | | | | X | | | | X | | X | | X |
| Radiological assessment | X ⁱ | | | | | | | | | | | | | |
| Immunogenicity assessments | | | | | | | | | | | | | | |
| Blood for PBMC assessment ^j | | X | | | | X | | X | | X | | X | | X |
| Blood for ctDNA assessment | | X | | | | | | | | | | | | X |
| Blood for PSA-binding antibody/anti-vector antibody/anti-antigen antibody assessment | | X | | | X | X | | | X | X | | | X | X |

Abbreviations: AESI – Adverse Event of Special Interest, C3=Cohort 3, ChAd=ChAdOx1-PCAQ, CRP=C-reactive protein, CT=computed tomography, ctDNA=circulating tumour DNA, d=day(s), ECG=electrocardiogram, ECOG=Eastern Cooperative Oncology Group, MVA=MVA-PCAQ, MRI=magnetic resonance imaging, PBMC=peripheral blood mononuclear cells, PET=positron emission tomography, PSA=prostate-specific antigen, SAE=serious adverse event

^a If the screening period is longer than 42 days, the participant must be reconsented. Consult with the Medical Monitor for which assessments should be repeated.

^b Windows during the intervention period are calculated from the date of the previous VTP-850 dose.

^c If a cardiac event is reported, blood should be taken for an additional assessment of troponin T and the participant should undergo an additional ECG and echocardiogram at the earliest opportunity.

^d Historic echocardiogram may be used if performed within 3 months of Day 1.

^e May be retrieved at any time during the intervention period.

^f If troponin T test result is abnormal, a re-test on the following day is required.

^g Pre-dose and approximately 30 min post-dose.

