8.1 Intervention Assessments

Participants will receive the relevant VTP-850 dose for their visit based on their Phase/cohort allocation, administered according to the pharmacy manual.

All participants will be observed in the clinic for at least 30 min post-dose in case of immediate AEs. The first participant in each Cohort should be observed for at least 60 min post each dose.

The following will be performed post-dose:

- Vital signs (pulse rate, blood pressure and temperature) will be measured at approximately 30 min post-dose
- The participant will be assessed for local or systemic reactions (e.g., change in vital signs, occurrence of pain or swelling at the injection site)

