8.4.7 Other Safety Assessments

On the day of each dose, during the telephone calls the day following administration of each component of VTP-850 and 7 days following the administration of ChAdOx1-PCAQ and at the 7-day post-dose visits following administration of MVA-PCAQ, the investigator will assess the injection/IV site and ask the participant how they are feeling since receiving VTP-850.

- If a participant experiences necrosis or exfoliative dermatitis at the injection site or requires an Emergency Room visit or hospitalisation for severe injection site pain, the investigator must immediately notify the sponsor and, if it is determined to be related to the administration of the trial intervention, further administration will be discontinued in that participant (see [Section 7.1](#)).
- To allow participants to obtain information on fever when not at site, they will be given a thermometer with instructions on how to measure temperature at home. Temperature will be measured at any time during the trial when fever is suspected. Fever is defined as a temperature of $\geq 38.0^{\circ}\text{C}$.

9 ADVERSE EVENTS, SERIOUS ADVERSE EVENTS, ADVERSE EVENTS OF SPECIAL INTEREST AND OTHER SAFETY REPORTING

Adverse events will be reported by the participant (or, when appropriate, by a caregiver, surrogate or the participant's legally authorised representative).

The investigator and any qualified designees are responsible for detecting, documenting and recording events that meet the definition of an AE, adverse event of special interest (AESI), or SAE and remain responsible for following up all AEs and SAEs that are considered related to the VTP-850 administration or trial procedures, or that caused the participant to discontinue VTP-850 or the trial.

The method of recording, evaluating, and assessing causality of AEs and SAEs and the procedures for completing and transmitting SAE/AESI reports are provided in [Appendix 3](#).

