2.2.1.1. Endpoints for the Primary Objective(s)

- Number and proportion of participants with AEs, treatment-related AEs, \geq Grade 3 AEs, \geq Grade 3 treatment-related AEs, serious adverse events, and treatment-related serious adverse events
- Number and proportion of participants with clinically significant laboratory values
- Change from baseline for laboratory tests, electrocardiogram and vital sign measurements at each time point of collection

Full details for each endpoint are provided in Section 6.7.

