5.1.4. Visit Windows

Tables 5 to 7 provides the relative study day ranges to be applied to the assessment / sample collection date to derive the analysis timepoint for by timepoint analyses of PSA / laboratory / vital signs and symptom-directed physical examination.

The following considerations are to be followed when deriving the analysis timepoints:

- The relative day number of the assessment lies between the lower and upper boundary of the visit window (the boundary values are included)
- Both scheduled and unscheduled assessments are included for visit windowing
- If there are two or more valid assessments for a defined window the following rules will be applied:
 - Assessments with missing data and assessments marked “Not Done” will be considered as providing a missing response and are not permitted to be assigned to a visit window.
 - The worst value (e.g. out of reference range preferred to within range; abnormal preferred to normal) will be used in each window. If multiple assessments fall within the same window with equal value, then the first non-missing value will be used for the summary.
- Participants who have an optional third dose of MVA-PCAQ due to an initial PSA response followed by progression will have an additional day 57, 64 and 71 visit. If two assessments are in both the additional day 64 and day 91 visit window or day 71 and day 91 visit window then the first assessment will be assigned to day 64 or 71 and the second to day 91. If only one assessment is available in both windows then this will be assigned to day 91.
- Participants who have had a study pause will not have visit windowing applied for visits after this window and will have analysis visit assigned based on the recorded visit name in the eCRF.

Table 4: Definition of Visit Windows for PSA Assessments

Period	Visit	Target Day of Visit	Protocol Visit Windows	Analysis Visit Window
Screening	Screening	Day -1 ^a	Day -43 to -1	Not Applicable
Intervention	Baseline	Day 1 ^a	Day 1 ^a	Prior to or on Day 1 ^a
Intervention	Day 29	Day 1 ^b	Day 1 ^b	Day 1 ^b
Intervention	Day 57	Day 1 ^c	Day 1 ^c	Day 1 ^c
Intervention	Day 64	Day 8 ^c	Day 5 to 9 ^c	Day 2 to 14 ^c
Intervention	Additional Day 57	Day 1 ^d	Day 1 ^d	Day 1 ^d
Intervention	Additional Day 64	Day 8 ^d	Day 5 to 9 ^d	Day 2 to 14 ^d
Intervention	Day 91	Day 91 ^a	Day 89 to 91 ^a	Day 78 to 104 ^a
Short-Term Follow-Up	Month 4	Day 120 ^a	Day 113 to 127 ^a	Day 105 to 135 ^a

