Table 6: Definition of Visit Windows for Vital Sign Assessments/Symptom-directed Physical Examination

Period	Visit	Target Day of Visit	Protocol Visit Windows	Analysis Visit Window
Screening	Screening	Day -1 ^a	Day -43 to -1 ^a	Not Applicable
Intervention	Baseline	Day 1 ^a	Day 1 ^a	Prior to or on Day 1 ^a
Intervention	Day 15	Day 15 ^a	Day 12 to 16 ^a	Day 11 to 27 ^a
Intervention	Day 29	Day 1 ^b	Day 1 ^b	Day 1 ^b
Intervention	Day 43	Day 15 ^b	Day 12 to 16 ^b	Day 11 to 27 ^b
Intervention	Day 57	Day 1 ^c	Day 1 ^c	Day 1 ^c
Intervention	Day 71	Day 15 ^c	Day 12 to 16 ^c	Day 11 to 27 ^c
Intervention	Additional Day 57	Day 1 ^d	Day 1 ^c	Day 1 ^c
Intervention	Additional Day 71	Day 15 ^d	Day 12 to 16 ^c	Day 11 to 27 ^c
Intervention	Day 91	Day 91 ^a	Day 89 to 91 ^a	Day 78 to 104 ^a
Short-Term Follow-Up	Month 6	Day 183 ^a	Day 176 to 190 ^a	Day 121 to 457 ^a
Long-Term Follow-Up	Month 24	Day 731 ^a	Day 724 to 738 ^a	Day 458 to 738 ^a

^a Relative to first dose of treatment

^b Relative to second dose of treatment

^c Relative to third dose of treatment

^d Relative to optional fourth dose of treatment

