6.7.4. Vital Signs

The analyses described below will be conducted for the following vital signs assessments respectively:

- systolic blood pressure (mmHg);
- diastolic blood pressure (mmHg);
- pulse rate (bpm);
- respiration rate (breaths / min);
- body temperature (°C).

In accordance with the baseline value definition in Section 5.1.2, the absolute change from baseline will be derived as follows:

Absolute change (unit) = (post-baseline value – baseline value)

Vital sign values will be considered as potentially clinically important (PCI) if they meet criteria listed in Table 10.

Table 10: Criteria for Potentially Clinically Important Vital Signs Parameters

Vital Sign	Criteria for observed value	Flag
Pulse Rate	<45 bpm	Low (L)
	≥45 and <120 bpm	Normal
	≥120 bpm	High (H)
Systolic Blood Pressure (SBP)	<90 mmHg	Low (L)
	≥90 and <160 mmHg	Normal
	≥160 mmHg	High (H)
Diastolic Blood Pressure (DBP)	<55 mmHg	Low (L)
	≥55 and <100 mmHg	Normal
	≥100 mmHg	High (H)

The following will be summarized by treatment group and overall for the Safety Analysis Set:

- Observed values and absolute change from baseline at each assessed timepoint for each standard vital sign parameter using default summary statistics for continuous variables;
- The worst absolute change (most extreme value, either increase or decrease) for each variable for each participant will be summarized using default summary statistics for continuous variables.
- Any post-baseline PCI result for each variable.
- If participants have PCI assessments, both below and above PCI criteria (as indicated in Table 10), participants are counted in both categories for summary tables.

A listing of all vital signs data including derived absolute change from baseline will be provided for the Safety Analysis Set.

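### On dosing days the SAP merges the pre-dose and 30-minute post-dose vital signs into one analysis value without fully defining which is kept, and temperature has no threshold.

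*SAP*

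**What the plan says.** **Collection.** A footnote to protocol Table 1 (section 1.3) times vital signs on Days 1, 29 and 57 as "Pre-dose and approximately 30 min post-dose". Protocol 8.1 names the variables: "Vital signs (pulse rate, blood pressure and temperature) will be measured at approximately 30 min post-dose".

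**Endpoint.** SAP 2.2.1.1 lists among the primary endpoints "Change from baseline for laboratory tests, electrocardiogram and vital sign measurements at each time point of collection".

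**Analysis timepoints.** SAP 5.1.4 says that its window tables set the analysis timepoint for by-timepoint analyses, vital signs included. The relevant table is Table 6, "Definition of Visit Windows for Vital Sign Assessments/Symptom-directed Physical Examination". It has one row each for Day 29, Day 57 and Additional Day 57, and each window is the day of that dose. When a window holds two or more valid assessments, "The worst value (e.g. out of reference range preferred to within range; abnormal preferred to normal) will be used in each window". If the values are equal, the first non-missing one is used.

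**Baseline.** SAP 5.1.2 takes the last non-missing value before first dosing and does not treat vital signs labelled post-dose on Day 1 as pre-dose. SAP 5.1.3 assigns them to the Intervention Period.

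**Summaries.** SAP 6.7.4 covers five variables, including body temperature. It plans "Observed values and absolute change from baseline at each assessed timepoint for each standard vital sign parameter", a worst change per participant, "Any post-baseline PCI result for each variable", and a full listing. The limits in Table 10 cover pulse, systolic and diastolic pressure only. Protocol 8.4.7 states: "Fever is defined as a temperature of" 38.0 °C or more.

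**The concern.** Pre-dose and post-dose are two collection points under the primary endpoint, but the SAP has one slot for them. The row labelled Day 29 or Day 57 will hold pre-dose values for some men and post-dose values for others, and the change shown has no clear meaning.

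The post-dose reading carries weight in this trial. Protocol Table 1 schedules vital signs on Days 29, 43, 57 and 71 and none on Days 36 or 64. The 30-minute value is therefore the only scheduled post-dose vital-sign reading until about 14 days after each boost. The ECGs on Days 29 and 57 are pre-dose. Protocol Table 3 reports a potential cardiac signal after the first MVA-PCAQ boost and names fever as a possible systemic reaction. Protocol 4.1.1 and 4.1.3 make the choice between the IM and IV boost depend on acceptable safety. A by-visit table that cannot separate before from after is of little use for that comparison.

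**Working it through.** The plan states no figure on this point, so there is none to reproduce. The check has two parts.

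**1. Following the rule as written on a boost day**

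- Both readings fall on Day 1 relative to that dose, so both lie in the single Table 6 window.
- Section 5.1.4 then keeps one value. If only the post-dose value is outside a limit, it is kept. If only the pre-dose value is outside, that one is kept.
- If both are in range and differ, the rule does not decide. Being out of range is given only as an example of *worst*, and the tie-break covers equal values only.
- Temperature has no limit in Table 10, so the range example gives no guidance for it.
- On Day 1 the post-dose reading is not baseline (5.1.2), and the next row in Table 6 is Day 15 (Days 11 to 27). It has no analysis timepoint.
- After a study pause, windowing stops and the eCRF visit name is used (5.1.4). The SAP does not say that this name separates the two readings.

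**2. How much the undefined word matters (illustration)**

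The documents give no vital-sign means or SDs. Assumed values:

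| Variable | Mean | Between-man SD | Within-man SD | Limits (Table 10) |
|---|---|---|---|---|
| Systolic pressure, mmHg | 135 | 12 | 7 | 90 to <160 |
| Pulse, bpm | 70 | 9 | 5 | 45 to <120 |
| Temperature, °C | 36.6 | 0.25 | 0.2 | none |

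Model: T is a man's usual level, Day 1 baseline = T + e0, pre-dose = T + e1, post-dose = T + d + e2, where d is the true post-dose shift. The tabulated change is the mean of (kept value - baseline) over 400,000 simulated men.

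- Reading A: keep the post-dose value only if it is out of range and the pre-dose value is not; otherwise keep the first (pre-dose) value.
- Reading B: keep the numerically higher value.

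| Variable | True shift d | Reading A | Reading B |
|---|---|---|---|
| Systolic | -10 | -0.1 | +0.8 |
| Systolic | +5 | +0.8 | +6.9 |
| Systolic | +10 | +2.0 | +10.8 |
| Systolic | +20 | +8.1 | +20.1 |
| Pulse | +5 | about 0 | +6.0 |
| Pulse | +10 | about 0 | +10.3 |
| Pulse | +20 | about 0 | +20.0 |
| Temperature | +0.5 | 0 | +0.5 |
| Temperature | +1.0 | 0 | +1.0 |

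Reading B can be checked by hand. Its expected change is d·Φ(d/θ) + θ·φ(d/θ), with θ = √2 × within-man SD. For systolic pressure θ = 1.414 × 7 = 9.90.

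- d = +10: 10 × 0.8438 + 9.90 × 0.2395 = 8.44 + 2.37 = 10.81.
- d = -10: -10 × 0.1562 + 9.90 × 0.2395 = -1.56 + 2.37 = +0.81.
- d = 0: 9.90 × 0.3989 = +3.95. Under Reading B a row with no drug effect still shows a rise of about 4 mmHg.

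With separate rows, the post-dose row shows the full shift (+10 as +10.0).

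Adding a 38.0 °C category without splitting the rows recovers little under Reading A: a true +1.0 °C is tabulated as +0.13 °C, with the post-dose value kept in 10.5% of men.

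**The case against.** The strongest reply is that the information is not lost.

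- SAP 6.7.4 also plans each participant's worst change for every variable, temperature included, a count of any post-baseline potentially clinically important (PCI) result, and a listing of all readings. Nothing there ties the first two to windowed values.
- A post-dose pulse or pressure that crosses a limit is kept when the pre-dose value is normal.
- Reactions reported as adverse events are tabulated for each administration within 28 days (SAP 6.7.2). Participants are telephoned the next day and given a thermometer (protocol 8.4.7).
- Protocol 11.2.2.3 plans a count of clinically significant vital-sign results.
- The SAP already recognises the post-dose label, and the table shells, which are not in the documents, may separate the rows.

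Most of this stands. A reader might infer that acute reactions to the boost are largely missing from the safety output, that the boost-day rows are always pre-dose, or that fever is counted nowhere. The documents support none of these. The outputs above remain, pre-dose selection is only one reading of *worst*, and fever reported as an adverse event is tabulated.

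Two points survive. The worst-change and PCI summaries do not attribute a result to a dose or to the post-dose reading. And shells that cannot be seen do not repair SAP text that defines the by-visit timepoints through Table 6.

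It is also fair that a same-day post-dose minus pre-dose contrast is an extra analysis; its absence is not an error.

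**Conclusion.** The point holds as a moderate reporting gap in a primary safety endpoint. Under any reading of *worst*, the one-value rule discards one of two planned boost-day readings from the by-visit table, and it leaves the choice undefined for in-range values and for variables without a range. An in-range post-dose rise may be hidden or shown in full, and a systolic fall of 10 mmHg was hidden under both readings tested. These sizes are illustrative and rest on the assumed means and SDs and on the two selection rules tried. The structural point rests on the text alone.

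Two further gaps are textual: the Day 1 post-dose reading has no row in Table 6, and Table 10 omits temperature although 6.7.4 promises a PCI result for each variable and the protocol supplies a fever definition. The raw data and the other summaries are intact, so the trial's ability to detect a reaction is not in question. What is missing is a by-visit table that shows when the change occurred relative to the dose.

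**What to change.** In the SAP:

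1. Table 6: use the eCRF label to give pre-dose and post-dose readings their own analysis timepoints. Add a post-dose row for Day 1 and both rows for Day 29, Day 57 and Additional Day 57. State that the one-value rule applies within each of these and not across them. State that the same split applies to visits assigned by eCRF name after a study pause.
2. Section 5.1.4: define *worst* for two in-range values and for variables without a range.
3. Table 10: add a body-temperature category that uses the protocol's own fever definition (38.0 °C or more). This adds to the row split and does not replace it.
4. Optional: summarise post-dose minus same-day pre-dose change by dose and treatment group.

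Cost: SAP and shell wording and a few extra table rows. No new data are needed.

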11.2.2.3 Vital Signs

Absolute and change from baseline vital sign results, including the worst change for each variable for each participant will be summarised using descriptive statistics. Treatment-emergent, out-of-range results with the corresponding normal ranges, baseline results and clinical significance will be listed separately. The number of participants with treatment-emergent, clinically significant results will be summarised.

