6.1. General Principles

All data processing, summarization and analyses will be performed using Fortrea's SAS Environment / Version 9.4 (or later) of the SAS® statistical software package.

The default summary statistics for quantitative variables will be the number of observations (n), mean, standard deviation (SD), median, 25th percentile, 75th percentile, minimum (min) and maximum (max), for those participants with data. The 25th and 75th percentiles will only be presented when the denominator is at least 10 participants.

For qualitative variables, the number (n) and percentage (%) of participants with non-missing data per category will be the default summary presentation, and where appropriate and present, the number of missing values as a “Missing” category. The number of participants in the analysis population will be used as the denominator for percentages calculation, unless stated otherwise in TFLs mock shell(s).

All statistical comparisons will be made using two-sided tests at the $\alpha=0.05$ significance level unless specifically stated otherwise. All null hypotheses will be of no treatment difference. All alternative hypotheses will be two-sided.

All laboratory test results will be received from central laboratories, and the results will be provided in both standard internal and conventional units. For the TFLs, the results will be summarized or presented in International System of Units (SI) units. Refer to Appendix of the TFLs mock shells for the SI unit corresponding to each laboratory test.

Refer to Appendix of the TFL shells for the precision level in which each laboratory test is reported by the central laboratories.

Specifications for table, figures and data listing formats can be found in the TFL shells specifications for this study. Please refer to “2. General Format Guidelines” section within TFL shells for more details on presentation of results.

In summary tables, participants will be presented by the following treatment groups::

- IM/IM Low Dose
- IM/IM Full Dose
- IM/IV Full Dose

If a participant does not receive a second dose of investigational product they will be assigned to the treatment group IM/IM Full.

In listings, participants will be presented by the following treatment groups:

- Cohort 1: IM/IM Low Dose
- Cohort 2: IM/IM Full Dose
- Cohort 3: IM/IV Full Dose

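### The worst-change row for vital signs mixes rises and falls, and the PCI count does not exclude abnormalities already present at baseline

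*SAP*

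**What the plan says.** **Worst change.** SAP Section 6.7.4 derives absolute change as the post-baseline value minus the baseline value, so it carries a sign. One value per man and variable then enters the summary: "The worst absolute change (most extreme value, either increase or decrease) for each variable for each participant will be summarized using default summary statistics". SAP Section 6.1 fixes what is shown: "The default summary statistics for quantitative variables will be the number of observations (n), mean, standard deviation (SD), median", then quartiles, minimum and maximum. It adds: "The 25th and 75th percentiles will only be presented when the denominator is at least 10 participants". Planned cohorts are 3–6 or 6 men (SAP Table 2), so at those sizes the cohort columns carry no quartiles. Protocol Section 11.2.2.3 also asks for each man's worst change but does not say how direction is to be handled.

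**PCI counts.** SAP Section 6.7.4 says: "Vital sign values will be considered as potentially clinically important (PCI) if they meet criteria listed in Table 10". Table 10 sets limits on the observed value for pulse, systolic pressure and diastolic pressure only. The summary is "Any post-baseline PCI result for each variable". A man with both low and high values appears twice: "participants are counted in both categories for summary tables". Baseline status plays no part.

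**Protocol.** Section 11.2.2.3, under the primary endpoint analysis, says: "The number of participants with treatment-emergent, clinically significant results will be summarised". It also asks for a separate listing of treatment-emergent out-of-range results alongside baseline results. SAP Section 7 records one change to the planned analysis, the added ECG endpoint.

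**The concern.** A single row that takes whichever change is larger, up or down, and then averages the signed values has no clear meaning in its mean or median. A value near 0 could mean that nobody moved, or that some men rose and others fell by a similar amount. For temperature and respiration rate, which have no PCI limits, this row is the only participant-level extreme in the summary tables.

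The PCI count has a different problem. The protocol asks what emerged on treatment. A count without a baseline condition also includes men whose abnormality was there before dosing and is seen again later. Such men can enrol, because exclusion criterion 22 on uncontrolled hypertension rests on the investigator's opinion and sets no numeric limit.

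SAP Section 4.3 places vital signs among the primary safety analyses. With 3–6 men per cohort, one man visibly changes a percentage.

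**Working it through.** The plan states no figure on this point, so there is none to reproduce. The check applies the SAP's rules to examples.

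**1. Offsetting in one cohort.** Take six hypothetical worst systolic changes: +25, +30, +20, −25, −30, −20 mmHg.
- Mean = (25 + 30 + 20 − 25 − 30 − 20)/6 = 0.
- Median = (−20 + 20)/2 = 0.
- SD = √[2(25² + 30² + 20²)/5] = √(3850/5) = 27.7.
- Minimum −30, maximum +30.
- Mean size ignoring sign = 150/6 = 25.

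The mean and median show nothing. The SD, minimum and maximum show movement both ways.

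**2. The same pattern in simulation.** The protocol's schedule gives 10 post-baseline readings up to Month 6: Day 1 post-dose, Day 15, Day 29 before and after dosing, Day 43, Day 57 before and after dosing, Day 71, Day 91 and Month 6. The documents give no within-man SD, so 5, 10 and 15 mmHg are assumptions. Baseline and each reading were drawn with that SD, in 20,000 cohorts of 6, with no drug effect:

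| Assumed SD (mmHg) | Mean signed worst change | Mean size of worst change | Mean largest rise | Mean largest fall |
|---|---|---|---|---|
| 5 | −0.03 | 12.0 | +7.7 | −7.7 |
| 10 | 0.02 | 24.1 | +15.4 | −15.4 |
| 15 | 0.17 | 36.1 | +23.2 | −23.0 |

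When 3 of 6 men rise by 20 mmHg and 3 fall by 20 mmHg at one visit, the mean signed worst change is −0.04, −0.03 and 0.04 for the three SDs. Its mean size is 20.8, 28.1 and 38.6 mmHg. With 8 readings instead of 10 the pattern is the same.

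**3. A shift in one direction.** Here changes were drawn directly with an assumed SD of 12 mmHg at 7 post-baseline visits. Adding a rise of 5 mmHg to every reading gives a mean signed worst change of about +15; adding 10 gives about +25. A common shift therefore shows. The row is still not an estimate of that shift, because it reports roughly two to three times its size.

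**4. PCI count in a planned cohort of 6.** Suppose a man has systolic pressure of at least 160 mmHg (the Table 10 limit) at baseline and again at a later reading.
- SAP rule: one such man gives 1/6 = 16.7%; two give 2/6 = 33.3%.
- Count restricted to men not beyond that limit at baseline: 0/6 = 0% in both cases.

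If no later reading meets the limit, he is not counted under either rule.

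**The case against.** The strongest reply is that little is lost. The primary endpoint as worded is change at each time point of collection (protocol Section 3, SAP Section 2.2.1.1), and the by-timepoint table delivers it. Low and high PCI values are counted separately, and every man's data are listed; with cohorts this small the listing can be read in full. For the no-effect case in step 3 (SD 12 mmHg, 7 visits), a cohort of 6 shows on average a minimum near −25, a maximum near +25 and an SD near 21, so two-way spread is visible. All of this stands. It rules out an inference that a reader might draw, that the SAP conceals hypertensive or hypotensive effects.

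A mean near 0 is also what one would expect with no effect, and separate rows would then show sizeable values produced by taking extremes of noise. That is right, and those rows need the same care in reading.

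A reader might take the signed worst change as an undeclared departure from the protocol. It is not one: the protocol leaves direction open. A reader might also take the PCI row to count the baseline reading itself. It does not, since the row is restricted to post-baseline values.

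Finally, PCI is a numeric threshold while the protocol speaks of clinical significance, and neither document defines treatment-emergent for vital signs; the SAP's definition covers adverse events only. Abnormalities judged clinically significant would usually also be recorded as adverse events (protocol Appendix 3). The table shells are not available, so a baseline PCI row may exist there. These points soften the contrast. They do not supply the treatment-emergent count that the protocol asks for.

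**Conclusion.** Two limited points hold.

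First, the mean and median of the worst-change row can offset rises against falls and are hard to interpret. Exact cancellation needs roughly balanced opposite movements across men. The other statistics in that row, the by-timepoint table and the listing are unaffected. This is a weak presentation choice.

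Second, the SAP replaces the protocol's treatment-emergent count with a count of any post-baseline PCI value, and Section 7 does not say so. Each man beyond a limit at baseline and again afterwards adds 16.7 percentage points in a planned cohort of 6. How many such men there are cannot be known from the documents.

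The cardiac signal described in protocol Section 2.3.1 might suggest that these tables are its main monitor. The documents assign that role to ECGs, blood tests, a baseline echocardiogram and special-interest event reporting. The effect here is on descriptive safety tables only: no test, alpha or sample size changes. It is a cheap improvement to one row and a correction to one count.

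**What to change.** In SAP Section 6.7.4:
- Replace the single worst-change row with two rows per variable: each man's largest increase and each man's largest decrease.
- Count a PCI result as treatment-emergent only when the baseline value did not meet the same limit in the same direction, and add a baseline-to-worst shift row.

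In Section 7, state that numeric PCI limits stand in for the protocol's clinically significant results, if that is the intention.

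SAP Section 6.7.3 already handles laboratory data this way, assessing two-directional toxicities separately and tabulating shifts from baseline. The cost is a few sentences and a few extra table rows. No further data need to be collected.
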